2. TRIAL DESIGN

A UK wide multicentre superiority cluster randomised controlled trial (cRCT) with nested process evaluation assessing IPV perpetration in 32 Probation Delivery Unit (PDU)/ Justice Social Work teams (JSWT) randomised to ADVANCE-D with community justice offender management (CJOM) compared to usual CJOM (1:1), combined with nested process evaluation. Outcomes of the ADVANCE-D Programme will be compared short (4 months), medium (12 months) and long-term (24 months) with usual CJOM for men who misuse substances convicted of IPV (serving a community sentence or on license post imprisonment) who

are subject to probation/ JSW supervision and are unsuitable for existing perpetrator interventions. Outcomes will also be collected from their current or ex-partners.

OBJECTIVES

2.1 PRIMARY OBJECTIVE

To assess whether ADVANCE-D with CJOM is superior to only CJOM in reducing IPV perpetration in the past 4 months at 12-months post-baseline, measured using the (Adapted) Abusive Behavior Inventory (ABI), compared to usual CJOM for men who misuse substances subject to probation/JSW supervision.

2.2 SECONDARY OBJECTIVES

- To assess whether ADVANCE-D with CJOM is superior to only CJOM at 4 and 12-months in reducing IPV victimisation, experienced by partners measured using the (Adapted) Revised Abusive Behavior Inventory (ABI-R).
- To assess whether ADVANCE-D with CJOM is superior to only CJOM at 4 and 12-months in improving other IPV outcomes: (Adapted) Revised Controlling Behaviors Scale (CBS-R), technology facilitated abuse, stalking/harassment, locked in, using children against partner, feeling of safety (women only), (Adapted) Intimate Partner Violence Responsibility Attribution Scale (IPVRAS) (men only); wellbeing: Patient Health Questionnaire (PHQ-9), Generalised Anxiety Disorder symptoms (GAD-7), Primary Care PTSD Screen for DSM-5 (PC-PTSD-5), Propensity for Abusiveness Scale (PAS) [anger subscale] (men only); self-control: Brief Self-Control Scale (BSCS) (men only); substance use: Treatment Outcomes Profile (partial), Alcohol Use Disorder Identification Test (AUDIT), Drug Use Disorder Identification Test (DUDIT); quality of life: EQ-5D-5L for participants and their current or expartners.
- To conduct a nested process evaluation to explore the implementation, mechanisms of impact, and contextual factors of delivering ADVANCE-D with participants and practitioners.
- To assess whether ADVANCE-D with CJOM is superior to only CJOM at 4 and 12-months in improving children's well-being as reported by men and their (ex)-partners.
- To compare costs and outcomes of ADVANCE-D with CJOM over and above usual CJOM using costconsequences analysis at 4 and 12-months.
- To link participants to routine databases and electronic records to compare health, social services, and criminal justice outcomes at 24-months between men offered ADVANCE-D with CJOM or usual CJOM and their (ex)-partners.

3. PARTICIPANTS

3.1 STUDY SETTING & RECRUITMENT

Courts mandate sentences to men convicted of IPV. Sentences include a rehabilitation activity requirement (RAR) in England; or a community payback order (CPO) in Scotland. These requirements/orders are given with a view to promoting the offender's rehabilitation and reduce the likelihood of reoffending. Men must see a Probation Practitioner (PP) at a Probation Delivery Unit (PDU; England)/ Justice Social Worker (JSW) at a Justice Social Work team (JSWT; Scotland) within 5 days post sentencing when sentence planning will take place. PDU/ JSW team make decisions on the offender management required to address any support recommended by court. Alongside the RAR or CPO, men will have a supervising PP/ JSW to monitor compliance to the community sentences. Any violation of conditions will be referred back to court.

There are 11 probation regions in England. PDU are the local units in each of these probation regions. For example, Greater Manchester (probation region) has 9 local PDU (see Table 1). Scotland has 32 Justice Social Work areas (JSW area) that provide statutory criminal justice services in JSWT. For example, City of Edinburgh (JSW area) has 2 local JSW teams (see Table 1). PDU and JSWT will be treated as clusters for the purpose of the trial.

To be eligible to take part in the trial, PDU and JSWT must have a central intervention delivery model (e.g. a central intervention delivery team in Greater Manchester deliver interventions across all 9 PDU); have trained and certified facilitators and partner support workers; and not be sites in other intervention trials. Facilitators in each Probation Region (England) and JSW area (Scotland) will be trained to centrally deliver the ADVANCE-D Programme and will be blind to allocation of PDU/ JSWT. Each PDU/ JSWT will recruit and consent 14 men to the trial before the outcome of allocation is known to them.

A total of 32 PDU/ JSWT are required for the cRCT. Twelve PDU/ JSWT (clusters) from the 24 clusters in Table 1 will be allocated at random for men to receive the ADVANCE-D Programme delivered by a central team + usual community justice offender management (CJOM) (Option 1) OR usual CJOM (Option 2) during the internal pilot from two probation regions from England (Greater Manchester and the North West) and one JSWT from Scotland (City of Edinburgh). An additional 20 PDU/ JSWT will be recruited to the main trial.

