10. STATISTICAL METHODS

A senior statistician will oversee the analysis conducted by the trial statistician performed using Stata version 18 (or later). A detailed statistical analysis plan (SAP) drafted by a Statistician following KCTU Standard Operating Procedures blinded to any outcome data and agreed with the TSC prior to assessing outcome data will ensure the study is conducted according to CONSORT guidelines.⁸⁴

The estimand framework will be described in full in the SAP and will cover the population, endpoint (ABI-Total Score), treatment condition (comparison of ADVANCE-D versus usual CJOM), intercurrent events (such as: suicide, all-cause mortality (non-suicide), returning to prison, and population summarise (adjusted mean difference). Rationale for the estimand is to describe the comparison between ADVANCE-D versus usual CJOM under routine practice.

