10.3 SAMPLE SIZE JUSTIFICATION

To detect an effect size of 0.4,^{85,86} with 90% power and 5% significance (2-sided), a sample of 266 is required for an individually randomised trial. To inflate to a cluster RCT design, by randomising 26 PDU/JSWT with an average cluster size of 13.5 and an ICC=0.03,⁸⁷ the number analysed is inflated to 358. To account for 18% drop out of both offenders³⁷ and PDU/ JSWT we will plan to randomise 32 PDU/ JSWT (1:1) and enrol 450 offenders (14 per PDU/ JSWT).

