10.4 STATISTICAL METHODS FOR PRIMARY AND SECONDARY OUTCOMES

10.4.1 STATISTICAL METHODS FOR PRIMARY OUTCOME

We will analyse the primary outcome using multi-level linear regression model, including assessments at 4 and 12 months to assess the difference in ADVANCE-D and control at 12-months (primary assessment time-point). Participants and PDU/JSWT will be fit as random effects, and pre-specified fixed effects for participant age, baseline IPV severity, and baseline ABI total score, and region. The adjusted mean difference (aMD) in the Abusive Behavior Inventory (ABI) total score between those from ADVANCE-D with CJOM compared to Usual CJOM will be presented with the associated two-sided confidence intervals (95% CI) and p-value, and intraclass correlation coefficient (ICC). The analysis will use the ITT population that will include all participants who were followed up at either the 4- or 12-month time-point. Pattern missingness will explore the missing data. A CACE will be developed as a sensitivity analysis to the primary analysis. Sensitivity analyses will be used for modelling the different intercurrent events. An additional sensitivity analysis will use the partner IPV data.

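### Variation between ADVANCE-D delivery teams, which exists in the intervention arm only, is in neither the primary model, the listed sensitivity analyses nor the sample size; if teams differ, the standard error may be too small

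*Protocol*

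**What the plan says.** **Delivery.** Protocol 3.1 and 3.2.6 make a central delivery model an entry condition for every PDU/JSWT, with a single Greater Manchester team serving all 9 of its PDU as the example. Section 3.1 adds: "Facilitators in each Probation Region (England) and JSW area (Scotland) will be trained to centrally deliver the ADVANCE-D Programme". Section 5.2 says that these facilitators do not supervise the men and will not know which PDU/JSWT a man attends, which fits staff who serve men from several units. Control men receive no ADVANCE-D delivery.

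**Primary model.** Section 10.4.1 states: "Participants and PDU/JSWT will be fit as random effects". The fixed effects include 'region', undefined there; section 5.1 uses the word for an urban/rural class. The sensitivity analyses in 10.4.1 and 10.11 cover compliance (CACE), intercurrent events and partner-reported data. None concerns delivery team.

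**Sample size.** Section 10.3 allows for clustering "by randomising 26 PDU/JSWT with an average cluster size of 13.5 and an ICC=0.03", with no component above the PDU/JSWT.

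**Target.** Section 10 states: "Rationale for the estimand is to describe the comparison between ADVANCE-D versus usual CJOM under routine practice".

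**The concern.** Randomisation is by PDU/JSWT, but delivery is organised one level higher and in one arm only. If one team treats men in several intervention clusters, those clusters share whatever makes that team better or worse than another. They are then not independent, although the model treats them as such.

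The region fixed effect does not settle this. It removes what intervention and control clusters of a region have in common. A team effect acts only on the intervention clusters, so it is in effect a region-by-treatment variance and stays in the estimated difference without entering its standard error. If 'region' means urban/rural class, the model has nothing at team level at all.

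At stake are the width of the interval for the adjusted mean difference in ABI total score and the error rate of the superiority test, when the result is read as applying to teams other than those in the trial.

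**Working it through.** **1. The plan's own figures (10.3).** Inputs: effect size 0.4, 90% power, two-sided 5%, ICC 0.03, mean cluster size 13.5, 26 clusters, 18% dropout.
- Individually randomised: the t-test formula gives 133 per arm, 266 in all, as stated ("with 90% power and 5% significance (2-sided), a sample of 266 is required for an individually randomised trial").
- Design effect: 1 + (13.5 − 1) × 0.03 = 1.375; 266 × 1.375 = 366 against the stated 358, about 2% apart. A size of 12.5 gives 266 × 1.345 = 358.
- Dropout: 358 / 0.82 = 437 against 450 enrolled; 26 / 0.82 = 31.7, so 32 clusters; 32 × 14 = 448.

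The plan's figures hold to within about 3%. The only clustering in them is at PDU/JSWT level.

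**2. What a team effect adds.** Set the total variance to 1. A cluster mean of m men has variance s² = 0.03 + 0.97/m. With K clusters split 1:1 within each of R regions, one team per region and team variance τ² in the intervention arm only:

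Var(difference) = 4s²/K + τ²/R

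The planned model estimates essentially the first term. For K = 26 and m = 13.5:
- s² = 0.03 + 0.97/13.5 = 0.1019; 4s²/K = 0.0157; SE = 0.125.
- τ² = 0.01, R = 5: 0.0157 + 0.0020 = 0.0177; SE = 0.133.
- τ² = 0.03, R = 3: 0.0157 + 0.0100 = 0.0257; SE = 0.160.

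If the team variance were counted, approximate power at effect 0.4 from Φ(0.4/SE − 1.96) would be 89%, 85% and 70% in these three cases.

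**3. Error rate.** R and τ² are assumptions; the documents give neither. Cluster means were simulated with treatment and region fixed effects, a zero average effect and a nominal 5% t test (20,000 runs per cell, m = 13.5). Cells show model SE / true SE, with type I error in brackets.

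| Clusters, teams | τ² = 0 | 0.005 | 0.01 | 0.03 |
|---|---|---|---|---|
| 26, 3 | 0.99 (5.4%) | 0.96 (5.7%) | 0.92 (7.0%) | 0.80 (11.3%) |
| 26, 5 | 1.00 (4.9%) | 0.98 (5.4%) | 0.96 (6.4%) | 0.88 (8.2%) |
| 26, 8 | 1.00 (5.1%) | 1.00 (5.2%) | 0.98 (5.6%) | 0.95 (6.0%) |
| 32, 3 | 0.99 (5.4%) | 0.95 (6.0%) | 0.90 (7.8%) | 0.77 (12.4%) |
| 32, 5 | 0.99 (5.0%) | 0.96 (5.9%) | 0.95 (6.3%) | 0.86 (8.9%) |
| 32, 8 | 1.00 (5.3%) | 0.98 (5.5%) | 0.97 (5.8%) | 0.92 (7.0%) |

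Larger team variances, with 32 clusters of 11.5 analysed men (450 × 0.82 / 32 = 11.5); ranges are across repeat simulations:

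| Teams | τ² = 0.02 | τ² = 0.05 |
|---|---|---|
| 3 | 9.5-10.1% | 16.2-17.0% |
| 5 | 7.1-7.4% | 10.6-11.1% |
| 8 | 5.8-6.2% | 7.8-8.6% |

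**4. What the region fixed effect does.** A region effect of variance 0.03 shared by both arms, with no team effect, leaves type I error at 4.8-5.2%. The fixed effect handles what the arms share. The tables show that it does not handle the one-arm part.

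**The case against.** **Sharing is not shown everywhere.** One team across a whole region is explicit only for Greater Manchester, and as an example. Section 4.1.2 requires 3 trained Probation Officers per PDU and section 4.1.1 has 2 facilitators per programme, so staffing could be partly specific to a PDU. Such effects already sit in the PDU/JSWT random effect. An area with one intervention cluster has no sharing between clusters; City of Edinburgh has only 2 JSW teams. This stands, and is why the point says that clusters *may* share facilitators.

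**The larger figures rest on strong assumptions.** Team variance of 0.02-0.05 is a between-team SD of 0.14-0.22, or 35-56% of the target effect of 0.4. Three teams matches the pilot areas only, and 20 more clusters are to join. This stands: the upper figures are the end of a range, not an expectation.

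**The null matters.** If ADVANCE-D did nothing for anyone, teams need not differ through it and the error would stay near 5%. Inflation needs a zero average effect with some teams helping and others harming. The point about interval width does not depend on that null.

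**The target may be the participating areas.** The routine-practice sentence supports an estimand that lists intercurrent events; it does not call the teams a sample. Inference to the average over participating areas is legitimate and needs no team variance. The sentence is compatible with the wider reading but does not settle it.

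**It could be left to the SAP.** A partially nested model could be specified there. But the protocol itself fixes the random effects and names the sensitivity analyses. The process evaluation (3.7.10) does not say that the team or facilitator for each man is recorded, and that is best captured prospectively.

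A reader might infer that the planned interval is simply too narrow, or that the test runs at 10-16%. The documents support neither: they give no number of teams, no team variance and no staffing plan per region.

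**Conclusion.** The gap is real and its effect conditional. Delivery is organised above the randomised cluster in one arm, and no term, listed sensitivity analysis or sample-size component reflects this. The standard error is too small only if teams differ in effectiveness and the result is meant to reach teams outside the trial.

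Under the assumed 3 to 8 teams, each shared by all intervention clusters of its region, the effect on type I error is small (about 5-8%) at team variance up to 0.01. It becomes material mainly when teams are few and the variance is 0.02 or more: up to about 11% with 5 teams and 17% with 3. This is a worthwhile, inexpensive improvement rather than an error that the documents prove.

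**What to change.** 1. Record the delivery team and facilitators for each intervention man as delivery happens.
2. In 10.4.1, define 'region' as probation region (England) or JSW area (Scotland), distinct from the urban/rural class in 5.1.
3. In 10.11, pre-specify a sensitivity analysis of the primary outcome that adds a random effect for delivery team in the intervention arm only (partially nested, small-sample degrees of freedom). Report its interval beside the primary one, with the effect by team.
4. In 10.3, state that the ICC of 0.03 covers PDU/JSWT clustering only.

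The cost is a few identifiers and one extra model. With few teams the team variance will be imprecise and the interval wider, so this belongs in a sensitivity analysis; the primary analysis and sample size stay unchanged.

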3.2 ELIGIBILITY CRITERIA

3.2.1 INCLUSION CRITERIA FOR PARTICIPANTS (MEN)

- 1. Adult (18+) men serving a community sentence or post imprisonment on license for IPV towards a female current or ex-partner.
- 2. Drugs or alcohol linked to criminogenic need recorded on OASys (England) or LS/CMI (Scotland)*.
- 3. Able to provide contact details for (ex)-partner victim of index crime will be invited to participate in the trial.
- 4. Able to communicate in and understand English for the purpose of research interviews.

[figure not shown]

Figure 1. Flowchart for probation practitioners to determine suitability for ADVANCE-D based on level of substance use

[figure not shown]

Figure 2. Flowchart for justice social workers to determine suitability for ADVANCE-D based on SARA V3

*Prisoner Offender Managers complete an initial Offender Assessment System (OASys) assessment within 10 weeks of being sentenced. The OASys measures eight criminogenic needs linked to offending behaviour including whether drugs or alcohol were linked to the offending behaviour. During the study timeframe, all men sentenced for IPV will be screened for eligibility for ADVANCE-D (Figure 3). Men who 1) have drugs or alcohol linked to criminogenic need recorded on OASys (England) or The Level of Service/Case Management Inventory (LS/CMI) (Scotland) AND 2) do not have substance use impairment (based on practitioner assessment of frequency/amount of substance use, impact of substance use on daily activities/functioning, and health, social, legal or financial problems as a result of substance use) on the substance use screen (Table 2) administered by probation practitioners in England, or based on SARA V3 in Scotland are suitable for ADVANCE-D. The use of Rehabilitation Activity Requirements (RAR) in England or unpaid work or other activities in Scotland, such as ADVANCE-D, should be considered for this group.

ADVANCE-D Version 6. 22/10/2024 EudraCT

Suitability screening tool for substance misuse interventions/treatment (v3)

rug and Alcohol Needs assessment	Acohol	Cannabis	Cocsine	Amphetamine	Inhalants	Hallucin ogens	Opioids	Other	
lease circle the score for each relevant s	ubstance				2		Ĩ		
	Never	0	0	0	0	0	0	.0	0
Q1. In the past 6 months, how often	Once/twice	2	3	3	3	3	3	3	3
have you used?	Monthly	3	4	4	4	4	4	.4	+
(If never, the remaining questions do	Weekly	4	5	\$	5	5	5	.5	5.
not need to be scored)	Daily/almost	*6*	*6*	*6*	*6*	*6*	*6*	*6*	*6*
	Never	0	0	0	0	0	0	0	0
Q2. In the past 6 months, how often	Once/twice	3	4	4	4	4	4	4	4
have you had a strong urge/ desire to	Monthly	4	5	5	5	5	5	5	5
use?	Weekly	5	6	6	6	6	6	6	6
	Daily/elmost	6	7	7	7	7	7	7	7
	Never	0	0	0	0	0	0	0	0
Q3. During the past 6 months, how often has your use led to health, social, legal or financial problems?	Once/twice	4	5	5	5	5	5	5	5
	Monthly	5	6	6	6	6	6	6	6
	Weekly	6	7	7	7	7	7	7	7
	Daily/almost	2	8	8	8	8	8	8	8
Q4. During the past 6 months, how		0	0	0	0	0	0	0	0
	Neuer	5	6		6	6	6	6	6
often have you failed to do what was	Once/twice	6	7	2	7	2	2	7	7
normally expected of you because of	Monthly	-			-	- 2	-		-
your use?	Weakly	7	8	. 1				1	
	Daily/almost		9	9.	9	9	9	9	9
	No, never	0	0	. 0	0	0	0	0	0
Q5. Has a friend/ relative or anyone else ever expressed concern about	Yes, in the past 6 months	6	7	7	7	7	7	7	70
your use?	Yes, but not in the past 6 months	1	4	4	4	4	4	4	4
Q6. Have you ever tried to cut down	No, never Yes, in the past 6	6	7	7	7	7	7	7	7
on your use but failed?	Yes, but not in the past 6 months	3	4	4	4	4	4	4	4

1. Interpreting the Score

Brief intervention/Intervention advised	11-26	4-26	4-26	4-26	4-26	4-26	4-26	4-26
Treatment required - DRR/ ATR assessment	27+	27+	27+	27+	27+	27+	27+	27+
Alcohol Abstinence Monitoring Requirement (AAMR)	0.26		2.5		- 1		- 1	

2. Court Assessments

2.1 Rehabilitation Requirement Activity Requirement (RAR)
Where an individual scores between 11-26, consider the use of RAR interventions for motivational interventions, advice, information, relapse prevention, constructive alternatives to substance misuse and assessment appointments. Brief interventions of this kind may be available antianally or could vary aroras Regions of Probation Delivery Units (2013). As such, it is imprestive that the Effective Proposal Framework (EFF) Tool is used to identify the available and eligible interventions. EFF can be accessed.

that the Checker Propose Prantowork (EPP) soon is used to interest, the available and engine interventions. EPP can be accessed.

Notes: #21Too!

Notes: #a individual scores below 27, but you feel there may be men't in pursuing an assessment for a DRR/ATR, please contact your local Treatment Provider for further discussion.

2.2 A Drug Rehabilitation or Alcohol Treatment Requirement.
Where an individual scores 27+ (*or if Q3 is scored 6+, regardless of the scores for remaining questions) for at least one of the substances listed above contact the Treatment Provider in the locality that the person will be supervised for further assessment. Please use the fine test below to provide information that you have gained that is relevant to the individual's substance misuse. This may include injecting behaviour and any mental health concerns (you may need to consider a combined order with a Mental Health Treatment Requirement). You will need to inform the Treatment Provider of your assessment of the level and nature of risk posed by the individual.

Note: A court can impose a DRR for any substance that is included in the Misuse of Drugs Act 1971. It is up to the court to decide Note: A court can impose a DRR for any substance that is included in the Misuse of Drugs Act 1971, it is up to the court to decide if they think that any substance used by a person is covered by this. However, a DRR can only be imposed if there is a test for the drug of choice available in the community. There is no test routinely available for Psychoactive Substances (PS) in the community currently. The court would need to be advised that making a person who only used PS subject to a DRR would not meet the requirements to impose such an intervention. Most people are poly drug users. If someone presents as using any substance that can be tested for (Opiates, Occaine, Amphetamines, Beroodiazepine and Cannabis) in combination with the above, a DRR can be recommended if agreed with a Treatment Provider.

[figure not shown]
Table 2. Suitability screening tool for substance use interventions

Probation Practitioners (England)/ Justice Social Workers (Scotland) check men's eligibility

In England, Probation Practitioner completes Offender Assessment System (OASys), SARA v2 and sentence planning. In Scotland, Justice Social Workers complete Level of Service/Case Management Inventory (LS/CMI), SARA v3 and sentence planning. Identification of men can also be done retrospectively.

- Adult (18+) men serving a community sentence or post imprisonment on license for IPV towards a female current or ex-partner
- Drugs or alcohol linked to criminogenic need recorded on OASys (England) or LS/CMI (Scotland)
- Able to provide contact details for (ex)-partner victim of index crime will be invited to participate in the trial
- Able to communicate in and understand English for the purpose of research interviews
- No history of sex offences against children
- Answers 'strongly disagree' to all 8 items on the eHealth Literacy Scale (eHEALS)
- Substance use does not impair ability to take part in the trial using the substance use screen (England) or SARA V3 (Scotland)
- Not suitable for existing probation-based perpetrator interventions
- Not involved with the private family law court

health, social and criminal justice data sets

Figure 3. Study flowchart

Figure 3 illustrates the different phases of the cRCT for male participants.

